1.5. Benefit-Risk Assessment

PH1 is a rare autosomal recessive disease characterized by excessive oxalate production by the liver leading to excessive urinary oxalate and varying types and degrees of renal disease, progressing to end-stage renal disease. Systemic accumulation of calcium oxalate results in severe end-organ damage. Without treatment, the disease progresses, and patients die from end-stage renal disease and/or complications of systemic oxalosis.

Lumasiran is designed to reduce hepatic production of oxalate. Based on the available data from nonclinical studies and the Phase 1/2 clinical study ALN-GO1-001, lumasiran, administered subcutaneously, demonstrated a potent, dose-dependent inhibition of glycolate oxidase resulting in decreased urinary oxalate and increased plasma and urinary glycolate. Unlike oxalate, glycolate is highly soluble and readily excreted in the urine. Thus, by reducing the production of oxalate, lumasiran is expected to ameliorate the signs and symptoms of PH1 and alter the clinical course in patients across the spectrum of disease, irrespective of age, disease stage, and status of dialysis dependence.

Based on the available safety data from the Phase 1/2 clinical study, lumasiran has been well tolerated with a favorable safety profile. Most adverse events (AEs) have been mild or moderate in severity. There have been no severe or serious adverse events related to study drug. Transient, mild injection site reactions (ISRs) have been observed but have not resulted in any treatment discontinuations. No clinically significant laboratory or hematologic changes have been observed.

Given the biological target of lumasiran, the available nonclinical and clinical data, and mode of administration, important potential risks for lumasiran are injection site reactions and liver function test abnormalities. During the study, patients will be closely monitored, including evaluation of injection sites, laboratory monitoring for liver function test abnormalities, along

with other standard hematology and blood chemistries. The study has specific inclusion and exclusion criteria to ensure that patients have adequate hepatic function and specific rules for dose withholding and stopping have been incorporated in the protocol for abnormalities in liver function tests. As the risk of embryofetal toxicity is currently unknown, females who achieve child-bearing potential during the study must have a negative pregnancy test, cannot be breast feeding, and must be willing to use contraception as specified in the protocol (see Section 5.5.1).

An external, independent Data Monitoring Committee (DMC) will monitor and ensure the safety of trial participants (see Section 3.7).

Based on the emerging efficacy and available safety data from the Phase 1/2 clinical study (ALN-GO1-001) and nonclinical studies, the benefit-risk assessment supports the evaluation of lumasiran in a Phase 3 study in PH1 patients of all ages (infants to adults) with advanced renal disease.

Detailed information about the known and expected benefits and risks of lumasiran are provided in the Investigator's Brochure.

2. OBJECTIVES AND ENDPOINTS

Objectives	Endpoints
Primary Cohort A 
Evaluate the effect of lumasiran on plasma oxalate in patients who are not on dialysis therapy Cohort B 
Evaluate the effect of lumasiran on plasma oxalate levels in patients who are on dialysis therapy	Cohort A 
Percent change in plasma oxalate from Baseline to Month 6 Cohort B 
Percent change in pre-dialysis plasma oxalate from Baseline to Month 6
Secondary 
Evaluate the effect of lumasiran on change in plasma oxalate area under the curve (AUC) between dialysis sessionsEvaluate the long-term effects of lumasiran on change in plasma oxalateEvaluate the effect of lumasiran on change in urinary oxalate excretionEvaluate quality of life in patients with PH1Characterize the PK of lumasiranEvaluate the effect of lumasiran on nephrocalcinosisEvaluate the effect of lumasiran on dialysis requirementsEvaluate the effect of lumasiran on the occurrence of renal stones	Primary Analysis Period (Baseline to 6 months) 
Percent change in plasma oxalate AUC between dialysis sessionsAbsolute change in plasma oxalateChange in the following parameters:
Urinary oxalate

Objectives	Endpoints

 Evaluate the effect of lumasiran on renal function Evaluate the effect of lumasiran on change in measures of systemic oxalosis 	
 QoL assessed by the PedsQL Total Score for patients ≥ 2 to <18 years of age at consent, and as assessed by KDQOL Burden of Kidney Disease and Effect of Kidney Disease on Daily Life subscales, and SF-12 Physical Component Summary and Mental Component Summary, in patients ≥ 18 years at consent Plasma PK parameters of lumasiran 
Long-term Extension Period (6 months to end of study)
 
 Percent change in plasma oxalate AUC between dialysis sessions Percent and absolute change in plasma oxalate Change in the following parameters: 
 Nephrocalcinosis as assessed by renal ultrasound Frequency and mode of dialysis Frequency of renal stone events Urinary oxalate Renal function as assessed by eGFR Measures of systemic oxalosis in the following systems: 
 Cardiac Dermatologic Skeletal Ocular QoL(Quality of life) assessed by the PedsQL Total Score for patients ≥ 2 to <18 years of age at consent, and as assessed by KDQOL Burden of Kidney Disease and Effect of Kidney Disease on Daily Life subscales, and SF-12 Physical Component Summary and Mental Component Summary, in patients ≥ 18 years at consent
Exploratory	

 Evaluate growth parameters and developmental milestones in patients who are <6 years of age at consent Evaluate quality of life in patients with PH1 Evaluate the effects of lumasiran on patient and caregiver resource use 	
 Growth parameters in patients who are <6 years of age at consent Change in developmental milestones over time in patients <6 years of age at consent Change in QoL as assessed by EQ-5D-Y and PedsQL (individual subscales of the generic and ESRD modules, and ESRD module total

Objectives	Endpoints

Describe patient experiences on lumasiran in PH1 patients and the experiences of caregivers for these patientsAssess for antidrug antibodies (ADA) against lumasiranEvaluate the effects of lumasiran on additional pharmacodynamic (PD) parameters of plasma glycolate and urinary glycolate	
score) for patients ≥ 2 to 18 years of age at consent, and as assessed by EQ-5D-5L in patients ≥ 18 years of age at consent
 
Change in QoL as assessed by KDQOL Symptoms and Problems of Kidney Disease subscale in patients ≥ 18 years of age at consentChange in patient and caregiver resource use (eg, work/school attendance, visits to doctor/hospital)Change in patient and caregiver experiences as evaluated by a patient experience questionnaire and a caregiver experience questionnaireFrequency of ADAChange in urinary and plasma glycolate
Safety	
Evaluate the safety and tolerability of lumasiranFrequency of adverse events

3. INVESTIGATIONAL PLAN

3.1. Summary of Study Design

This is a multicenter, single arm study designed to evaluate the efficacy, safety, PK and PD of lumasiran in patients with a documented diagnosis of PH1 who have advanced renal disease, as evident by eGFR ≤ 45 ml/min/1.73 m². All eligible patients will be administered lumasiran; no control group will be assessed.

This study will include 2 cohorts: Cohort A and Cohort B. Cohort A will include patients who do not yet require dialysis. Cohort B will include patients who are on dialysis therapy. Dialysis modality will be restricted to patients on hemodialysis. Patients on a combination of peritoneal and hemodialysis, and patients on peritoneal dialysis only will be excluded from the study. Enrollment to both cohorts will occur concurrently. Cohort A patients who experience progression of renal impairment over time and begin to require dialysis therapy will cross-over to Cohort B.

Patients will be screened from Day -120 to Day -1 to determine eligibility. Consented patients meeting all eligibility criteria will receive their first dose of lumasiran on Day 1. Lumasiran will be administered subcutaneously (SC) utilizing weight-based dosing, with dose adjustments for interval weight gain, as specified in Section 5.2.2.

Patients will return to the clinical center for follow-up assessment of efficacy, safety, and PK, and other procedures according to the Schedule of Assessments through the last study visit. Safety assessments will include collection of AEs, clinical laboratory tests, vital sign

assessments, electrocardiograms (ECGs), physical examinations, and concomitant medications. Dialysis status and changes in dialysis regimen will be monitored. During periods of time when the COVID-19 pandemic impedes the ability of patients to travel to the study site, visits by a healthcare professional may occur at an offsite location such as the patient's home).

Blood samples will be collected in both cohorts for PK parameter analysis, plasma oxalate sample analysis, and to establish plasma oxalate profiles (in Cohort B only; the profile enables AUC calculation between dialysis sessions) (Table 5, Table 6). From Screening to Day 1, patients will have at least 4 plasma oxalate collections (pre-dialysis in Cohort B) to establish a robust baseline measurement. The plasma oxalate sample collection during Screening is described per cohort in Figure 1, and during the treatment period will be performed as per the Schedules of Assessments (see Table 1, Table 2, Table 3, and Table 4).

Patients who are anuric are defined as producing <100 ml of urine per day. For all patients who are not anuric (ie, can produce \geq 100 ml of urine per day), single-void urine samples (in triplicate) will be collected during screening to establish baseline and then serially per the Schedules of Assessments.

For patients able to provide 24-hour urine samples, three 24-hour urine collections will be scheduled during screening to establish baseline urinary oxalate levels. At Month 6, three 24-hour urine collections will be scheduled within 14 days prior to dose. There will be a single 24-hour urine collection at Month 3, Month 12, and every 6 months thereafter while on study.

This study will consist of 2 periods: a 6-month primary analysis period followed by a long-term extension period. During the 6-month primary analysis period, patients will undergo efficacy and safety assessments every 2 weeks for the first month and monthly thereafter. During the long-term extension period of up to 54 months, dosing will continue and visits will occur at least every-3-months.

Patients who discontinue study drug early will be asked to return for follow-up visits as described in Section 4.3.1.

3.2. Duration of Treatment

The duration of treatment with lumasiran is up to 60 months, with final dose administered at the Month 57 visit.

3.3. Duration of Study

The estimated total time on study, inclusive of screening, for each patient is up to 64 months, including up to 120 days of screening followed by up to 60 months of treatment, with a month defined as 28 days.

3.3.1. Definition of End of Study for an Individual Patient

A patient is considered to have reached the end of the study if:

- the patient has completed the end of study (EOS; Month 60) visit, or
- the patient has completed 12 months of monitoring following the final lumasiran dose

3.4. Number of Planned Patients

The planned enrollment for this study is 20 patients, including 6 patients in each cohort. Of those 20 patients, the planned enrollment includes 4 patients who are <6 years of age at consent, and 2 patients between ≥ 6 to <18 years of age at consent.

Patients who crossover from Cohort A to Cohort B (due to progressing to dialysis therapy), discontinue study drug, or stop participation in the study prior to completion of Month 6 assessments may be replaced (see Section 4.3.4).

3.5. Method of Assigning Patients to Treatment Groups

Patients will all be assigned to 1 single treatment group. Dosing will be determined by the patient's weight (see Section 5.2.2).

Each patient will be uniquely identified in the study by a combination of the site number and patient identification number. Upon signing the informed consent form (ICF), the patient will be assigned a patient identification number by the interactive response system.

3.6. Blinding

Not applicable.

3.7. Data Monitoring Committee

An independent Data Monitoring Committee (DMC) will oversee the safety and overall conduct of this study, providing input to the Sponsor. Additional assessments may be recommended by the DMC. The DMC will operate under the rules of a charter that will be reviewed and approved by the DMC. Details are provided in the DMC Charter.

4. SELECTION AND WITHDRAWAL OF PATIENTS

4.1. Inclusion Criteria

Patients are eligible to be included in the study if all the following criteria apply:

4.1.1. Cohorts A and B

Age

1. Have reached at least 37 weeks estimated gestational age (full-term infant) at consent (or assent).

Patient and Disease Characteristics

2. Documentation or confirmation of PH1 as determined by genetic analysis prior to initial dosing.
3. Patients with eGFR ≤ 45 mL/min/1.73 m² as calculated by the MDRD formula if ≥ 18 years or Schwartz Bedside Formula if ≥ 12 months to <18 years, or patients <12 months of age with serum creatinine that is considered elevated for age at consent.

4. The mean of the three most recent screening plasma oxalate samples collected prior to Day 1 is $\geq 20 \mu\text{mol/L}$. In Cohort B, these 3 collections may include the first pre-dialysis sample from each plasma oxalate profile.
5. If taking therapeutic vitamin B6 (pyridoxine), must have been on stable regimen for at least 90 days before consent, and is able and willing to remain on this stable regimen until at least the Month 6 visit. Dose adjustments for interval weight gain are acceptable.

Informed Consent

6. Patient is willing and able to comply with the study requirements and to provide written informed consent. In the case of patients under the age of legal consent, the legal guardian(s) must provide informed consent and the patient should provide assent per local and national requirements.

4.1.2. Cohort B Only

1. On a stable hemodialysis regimen for at least 4 weeks prior to Screening plasma oxalate assessment; able and willing to maintain this regimen through Month 6 visit, with changes to dialysis regimen permitted only when medically indicated.

4.2. Exclusion Criteria (Cohorts A and B)

Patients are excluded from the study if any of the following criteria apply:

Laboratory Assessments

1. Has any of the following laboratory parameter assessments at Screening:
 - a. Alanine aminotransferase (ALT) or aspartate aminotransferase (AST) $>2 \times \text{ULN}$ for age
 - b. Total bilirubin $>1.5 \times \text{ULN}$. Patients with elevated total bilirubin that is secondary to documented Gilbert's syndrome are eligible if the total bilirubin is $<2 \times \text{ULN}$
 - c. International normalized ratio (INR) >1.5 for patients not on anticoagulants. Patients on oral anticoagulants (eg, warfarin) with an INR <3.5 will be allowed.
 - d. Hemoglobin $<8.0 \text{ g/dL}$
2. Has known active human immunodeficiency virus (HIV) infection; or evidence of current or chronic hepatitis C virus (HCV) or hepatitis B (HBV) infection.

Prior/Concomitant Therapy

3. Received an investigational agent within the last 30 days or 5 half-lives, whichever is longer, prior to the first dose of study drug, or are in follow-up of another clinical study during Screening. Consultation with the Medical Monitor is required if treated with unapproved products prior to consent regardless of the time interval prior to the first dose of study drug.

Medical Conditions

4. Known history of allergic reaction to an oligonucleotide or GalNAc.
5. Diagnosis of conditions other than PH1 contributing to renal insufficiency such as glomerulonephritis, nephrotic syndrome, or lupus nephritis.

6. Any condition or comorbidity, which in the opinion of the Investigator, would make the patient unsuitable for dosing or would interfere with study compliance, data interpretation, patient safety, and/or patient participation in the study. This includes significant active and poorly controlled (unstable) cardiovascular, neurologic, gastrointestinal, endocrine, renal or psychiatric disorders unrelated to PH1 identified by key laboratory abnormalities or medical history.
7. Unwilling or unable to limit alcohol consumption throughout the course of the study. Alcohol intake of >2 units/day is excluded during the study (unit: 1 glass of wine [approximately 125 mL] = 1 measure of spirits [approximately 1 fluid ounce] = ½ pint of beer [approximately 284 mL]).
8. History of alcohol abuse, within the last 12 months before screening, in the opinion of the investigator.
9. Patients with a previous liver transplant or for whom a liver transplant is anticipated in the next 6 months.
10. Patients with a previous kidney transplant who are currently receiving immunosuppression to prevent transplant rejection.
11. Patients maintained on a peritoneal dialysis regimen.
12. Patients who in the opinion of the Investigator plan to start dialysis replacement therapy in the next 6 months.
13. Any comorbidity or condition that, in the opinion of the Investigator, is anticipated to prevent participation in at least 12 months of the study.

Contraception, Pregnancy, and Breastfeeding

14. Is not willing to comply with the contraceptive requirements during the study period, as described in Section 5.5.1.
15. Female patient is pregnant, planning a pregnancy, or breast feeding.

4.3. Removal from Study Drug or Assessment

Patients or their legal guardians are free to discontinue study drug and/or stop protocol procedural assessments, or participation in the study as a whole at any time and for any reason, without penalty to their continuing medical care. The Investigator or the Sponsor may discontinue study drug or stop a patient's participation in the study at any time if this is considered to be in the patient's best interest. Any discontinuation of treatment or the stopping of the patient's participation in the study must be fully documented in the electronic case report form (eCRF) and should be followed up by the Investigator.

Discontinuation of study drug or declining procedural assessments is described in Section 4.3.1, while the stopping of a patient's participation in the study is detailed in Section 4.3.2.

4.3.1. Discontinuation of Study Drug or Declining Procedural Assessments

Reasons for discontinuation of study drug may include any of the following:

- Significant violation of the protocol

- AE
- Non-adherence to treatment regimen
- Pregnancy
- Lost to follow-up
- Other reason (non-AE)
- Or, study is terminated by the Sponsor

If possible, the Investigator will confer with the Sponsor or Medical Monitor before discontinuing dosing in the patient. Patients who are pregnant will be discontinued from study drug dosing immediately (see Section 6.5.6.7 for reporting and follow-up of pregnancy). A positive urine pregnancy test should be confirmed by a serum pregnancy test prior to discontinuing the study drug.

If a patient discontinues dosing due to an AE, including SAEs, the event should be followed as described in Section 6.5.6. When a patient discontinues study drug dosing, the primary reason must be recorded in the electronic case report form (eCRF). Patients who discontinue study drug and remain on study may receive treatment consistent with local standard practice for their disease per Investigator judgement, as applicable.

Patients who discontinue from study drug during the 6-month primary analysis period (defined as the time the first dose of study drug is administered on Study Day 1 through completion of the Month 6 assessments) will be encouraged to remain on the study and complete assessments (including 24-hour urine collections, but excluding PK assessments) through Month 6 (see Table 1). They will also be asked to complete safety follow-up visits, once every 3 months, per the safety follow-up schedule (see Table 3 or Table 4) for up to 12 months after the last dose of lumasiran.

Patients who discontinue study drug after Month 6 will be asked to return for their next scheduled visit to complete early termination (ET) assessments and complete safety follow-up visits, once every 3 months, per the safety follow-up schedule (see Table 3 or Table 4) for up to 12 months after the last dose of lumasiran.

4.3.2. Stopping a Patient's Study Participation

4.3.2.1. Patient or Legal Guardian Stops Participation in the Study

A patient or their legal guardian may stop participation in the study at any time. A patient or legal guardian considering stopping participation in the study prior to the Month 6 visit should be informed that the patient can discontinue study drug and/or decline procedural assessments and remain in the study to complete their study assessments, through the Month 6 visit, including follow-up, or alternatively may complete any minimal assessments for which the patient or legal guardian consents as described in Section 4.3.1. If a patient or legal guardian still chooses to discontinue study drug and stop participation prior to the completion of the 6-month treatment period, every effort should be made to conduct early the assessments scheduled to be performed at the Month 6 visit (see Table 1).

If the patient does not wish to or is unable to continue further study participation, the Investigator is to discuss with the patient appropriate procedures for stopping participation in the study. Data collected from the patient can continue to be used, in countries where permitted.

In addition, in the countries where the collection and processing of the patient data is based on the patient consent, if a patient withdraws consent to collect and process his/her data (see Section 4.3.2.2), as applicable, patient data up to the withdrawal of consent will be included in the analysis of the study. In addition, where permitted, publicly available data (such as appropriate national or regional vital status registry or other relevant databases) can be included after withdrawal of consent, where available and allowable by local law.

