4. PATIENT POPULATION

4.1. Patient Definitions

The populations (analysis sets) are defined as follows:

- Safety Analysis Set: All patients who received any amount of lumasiran during study.
- Full Analysis Set: All patients who received any amount of lumasiran and have at least one evaluable plasma oxalate value (pre-dialysis in Cohort B) at baseline and at least one evaluable plasma oxalate value from assessment(s) at Month 3 through Month 6
- PK Analysis Set: All patients who received any amount of lumasiran, have at least 1 postdose blood sample for PK parameters, and have evaluable PK data.

The Safety Analysis Set will be used for safety analyses and the sensitivity analysis of efficacy. The Full Analysis Set will be used to evaluate efficacy endpoints. The PK Analysis Sets will be used to conduct PK analyses.

This study will consist of 2 periods: a 6-month Primary Analysis Period followed by a long-term (54 months) extension period. The Primary Analysis Period starts at the first date/time of lumasiran dose administration and ends at either the date/time of lumasiran dose administration at Month 6 (exception being that Month 6 assessments (eg, plasma oxalate and PK assessments) which occur after the Month 6 dose will be included) or the date of the Month 6 visit (Day 169) for patients who discontinued treatment prematurely. Primary analysis will be conducted using the Primary Analysis Period data collected through 6 months.

The Long-term Extension Period, starts at the date/time of lumasiran dose administration at Month 6 and is through the end of the study. Analysis of the Long-term Extension Period will focus on long-term efficacy and safety effects of lumasiran.

Patients who discontinue from study drug during the 6-month Primary Analysis Period (defined above) will be encouraged to remain on the study and complete assessments (including plasma oxalate but excluding PK assessments) through Month 6. They will also be asked to complete safety follow-up visits, once every 3 months, per the safety follow-up schedule for up to 12 months after the last dose of lumasiran.

Patients who discontinue study drug after Month 6 will be asked to return for their next scheduled visit to complete early termination (ET) assessments and complete safety follow-up visits, once every 3 months, per the safety follow-up schedule for up to 12 months after the last dose of lumasiran.

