5.6. Visit Windows

For tabular and graphical summaries, all data will be tabulated and analyzed per the evaluation visit as recorded on the electronic case report forms (eCRF) even if the assessment is outside of window.

Unless otherwise specified, data collected at an unscheduled visit will be included in by-patient listings and/or spaghetti plot figures, but no assignment of the scheduled visit will be made for the purposes of summary tabulations. However, unscheduled study visits will be used in the calculation of baseline values if prior to first dosing and for any categorical shift tables (eg shift from baseline to worst post-baseline value).

The following are time windows for the analysis of Plasma Oxalate Profile samples in Cohort B:

Blood Collection Sampling time	Window
Pre-Dialysis	Prior to dialysis on the same day as the dialysis
30 minutes before end of dialysis	from 1 hour prior to end of dialysis through the end of dialysis
30 minutes post-dialysis	after the end of dialysis through 1 hour post-dialysis
2 hours post-dialysis	>1 hour post-dialysis through 3 hours post-dialysis
4 hours post-dialysis	>3 hours post-dialysis through 6 hours post dialysis
8 hours post-dialysis	>6 hours post-dialysis through 10 hours post-dialysis
12 hours post-dialysis	>10 hours post-dialysis through 16 hours post-dialysis
24 hours post-dialysis	>18 hours post-dialysis through pre-dialysis the next day (if dialysis session scheduled day after current dialysis) or 29 hours post-dialysis (if no dialysis session scheduled day after current dialysis)

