6. STUDY ANALYSES

6.1. Patient Disposition

Number and percentage of patients will be tabulated by Cohort for the following categories:

- Safety Analysis Set
- Full Analysis Set
- PK Analysis Set

Summaries of the number and percentage of patients who discontinued treatment and/or withdrew from the study will be presented, along with the primary reasons for discontinuation of treatment and/or withdrawal from the study. Additionally, the number of patients who completed the Month 6 visit will also be displayed. A patient is defined as having completed the Month 6 visit if the patient has at least one blood sample for plasma oxalate (Cohort A) or pre-dialysis plasma oxalate (Cohort B) for the Month 6 visit.

An individual patient is considered to have reached the end of the study if:

- the patient has completed the end of study (EOS; Month 60) visit, or
- the patient has completed 12 months of monitoring following the final lumasiran dose.

The number and percentage of patients enrolled by country and site will be summarized.

Data listings of those patients who withdrew and/or discontinued treatment including the associated reasons will also be presented. Disposition will be summarized throughout the study. All disposition analyses will be presented by cohort.

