7.1. Primary Endpoint

The primary objective in Cohort A is to evaluate the effect of lumasiran on plasma oxalate in patients who are not on dialysis therapy. The primary objective in Cohort B is to evaluate the effect of lumasiran on pre-dialysis plasma oxalate levels in patients who are on hemodialysis therapy. The primary endpoint is percent change from baseline in plasma oxalate (Cohort A) / pre-dialysis plasma oxalate (Cohort B) to Month 6.

The primary analysis in Cohort A will be performed using a restricted maximum likelihood (REML) based Mixed-effect Model Repeated Measures (MMRM) approach using the FAS. Analysis will include evaluable plasma oxalate values of all scheduled visits through Month 6, which will be modeled with fixed effects of scheduled visits and baseline plasma oxalate, including patient as a random factor. Autoregressive (1) will be used to model the within-patient error given the small sample size for this study. The primary estimate is the least square (LS) mean of the percent change in plasma oxalate from baseline at Month 3 to Month 6, averaged over these timepoints. This LS mean will be presented along with corresponding standard errors (SEMs), 95% confidence intervals (CI) and p-value from the model (ie, testing against the null hypothesis of mean of primary outcome being equal to 0).

If the fit of the autoregressive (1) covariance structure matrix fails to converge, the primary estimate is the LS mean of the primary outcome variable average across scheduled visits from Month 3 to Month 6, according to analysis of covariance (ANCOVA) model with covariate of baseline plasma oxalate. This LS mean will be presented along with corresponding SEMs, 95% CI and p-value from the model.

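### A plasma oxalate sample taken before Month 3 at an early withdrawal can enter the Month 3 to Month 6 primary estimate if the visit is recorded as Month 6

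*Protocol*

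**What the plan says.** - **Early assessments.** Protocol 4.3.2.1 covers a patient who stops both drug and participation before Month 6. It asks that "every effort should be made to conduct early the assessments scheduled to be performed at the Month 6 visit" and points to Table 1. It sets no earliest day.
- **Schedule.** Table 1 runs from Screening to Month 6 and has no early-termination column. In the schedules, ET appears as a column only with Month 60 (Tables 3 and 4). Protocol 4.3.1 describes ET assessments for patients who stop drug after Month 6.
- **Visit assignment.** Under SAP 5.6, data in tables and figures are "analyzed per the evaluation visit as recorded on the electronic case report forms (eCRF) even if the assessment is outside of window". The only analysis windows given there are hours around dialysis for the oxalate profile. For unscheduled visits, "no assignment of the scheduled visit will be made for the purposes of summary tabulations".
- **Full Analysis Set.** Besides dosing and a baseline value, SAP 4.1 requires "at least one evaluable plasma oxalate value from assessment(s) at Month 3 through Month 6".
- **Primary estimate.** SAP 7.1 takes the least squares "mean of the percent change in plasma oxalate from baseline at Month 3 to Month 6, averaged over these timepoints". If the model does not converge, it uses ANCOVA on "the primary outcome variable average across scheduled visits from Month 3 to Month 6".
- **Completion.** SAP 6.1: "A patient is defined as having completed the Month 6 visit if the patient has at least one blood sample" for that visit, again with no day limit.

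**The concern.** The primary estimate is meant to describe plasma oxalate from Month 3 on, after the three monthly loading doses. A sample drawn after one or two doses measures something else. If it carries the Month 6 label, SAP 5.6 keeps it there whatever its study day.

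Three things could then go wrong. The average over Months 3 to 6 includes a value from before that interval. A patient with no true data from Month 3 onward joins the primary analysis set, although SAP 7.1.1 shows that such patients were meant to appear only in the Safety Analysis Set sensitivity analysis. And the count of Month 6 completers is too high. The sensitivity analysis would not expose this, because it would use the same value under the same label.

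Cohorts may be as small as 6, so one patient carries visible weight.

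**Working it through.** There is no planned figure to reproduce: SAP 5.1 sets 20 patients, at least 6 per cohort, on feasibility, with no effect size or SD. The check therefore has a reading part and an illustration on assumed figures.

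**1. Does any rule stop the value?** The evaluability rules in SAP 5.5 concern dialysis start or change, transplant and prohibited treatment, not study day. SAP 4.1 ends the Primary Analysis Period at Day 169 for early discontinuers, which bounds the period but does not relabel an earlier sample. SAP 7.8.2 only notes out-of-window values in a listing. The unscheduled-visit rule in SAP 5.6 is the one provision that keeps the value out, and it depends on how the visit is recorded.

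**2. Visit days.** Day = 28 × month + 1 gives Month 3 = Day 85 and Month 6 = Day 169, as in Table 1. The Month 6 window is Days 162 to 176 (±7), or 155 to 183 under the COVID-19 allowance (±14). A Day 29 sample recorded as Month 6 is 169 - 29 = 140 days early.

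**3. Size.** Assumptions, none from the documents:
- True mean change of -15% at Month 1, -30% at Month 2 and -40% from Month 3.
- One patient leaves at about Day 33 with -15% at Month 1 and -15% recorded as Month 6. All others have complete data.
- Between-patient SD 10 to 20 points, within-patient SD 10 to 15 points, AR(1) correlation 0.3, baseline covariate omitted.

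*Mixed model.* With visit as a fixed effect, a random patient effect and AR(1) errors, the shift is the generalised least squares weight of the early value times its shortfall, 40 - 15 = 25 points.

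| n | Weight | Shift = 25 × weight | Estimate (true -40) | Model SE |
|---|---|---|---|---|
| 6 | 0.083 to 0.105 | 2.1 to 2.6 | -37.9 to -37.4 | 4.9 to 9.2 |
| 10 | 0.050 to 0.063 | 1.2 to 1.6 | -38.8 to -38.4 | 3.8 to 7.1 |
| 14 | 0.036 to 0.045 | 0.9 to 1.1 | -39.1 to -38.9 | 3.2 to 5.9 |

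At correlation 0.7 and n = 6 the estimate is -37.3 to -37.2, a shift of 2.7 to 2.8. If the early value is not labelled Month 6, the estimate is -40.0 in every case.

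*ANCOVA fallback.* Ignoring the covariate, each patient has weight 1/n. At n = 6: (5 × -40 - 15)/6 = -35.8, a shift of 4.2 points. At n = 14: (13 × -40 - 15)/14 = -38.2, a shift of 1.8 points.

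*Other shortfalls.* The shift is proportional to the shortfall. For 20, 40 and 60 points at n = 6, the fallback moves by 20/6 = 3.3, 40/6 = 6.7 and 60/6 = 10.0 points.

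**The case against.** **The label is not known.** A reader might infer that early-withdrawal samples are always analysed as Month 6. The documents do not support that, because the eCRF is not among them. A visit recorded as unscheduled is kept out of scheduled-visit summaries by SAP 5.6. Protocol 6.5.5.1 also mentions an Early Termination visit without limiting it to after Month 6, so an ET label is possible. SAP 5.5 uses Months 3-6 partly as a span of time, which would argue against admitting a Day 33 sample. This objection stands as a condition on the point. It does not remove it: the protocol ties these assessments to Month 6, Table 1 offers no other column, and the outcome should not depend on an unstated recording choice.

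**The trigger is narrow.** The patient must leave the study, not just the drug, before about Month 3, and still agree to the assessments. Patients who only stop drug are encouraged to keep the normal schedule through Month 6. Exclusion criterion 13 also removes patients expected not to manage 12 months. This stands. A patient leaving between Month 3 and Month 6 gives a value that already belongs to the averaged interval, so little harm follows.

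**The shift is modest and visible.** At correlation 0.3 it is about 0.2 to 0.5 of the model's standard error, and usually toward less reduction. Withdrawals, protocol deviations and individual plots are all to be shown, so one case among 20 would be noticed. This stands too, and it limits the weight of the point. But noticing the case after the fact leaves its handling to a decision made with the data in view. Replacing the patient under Protocol 4.3.4 does not remove the value.

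**Conclusion.** The point holds conditionally. If the early assessments are recorded on the eCRF as Month 6, the written rule in SAP 5.6 puts a sample from before Month 3 into the primary estimate, and SAP 4.1 and 6.1 then admit the patient to the Full Analysis Set and count a Month 6 completer. If they are recorded as unscheduled or ET, this would not happen.

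On the assumed figures, one such patient moves the mixed-model estimate by about 2 to 3 points with 6 patients and about 1 point with 14, and the ANCOVA fallback by about 4 points with 6. The size rests on the assumed 25-point shortfall and variance components, since the documents give neither.

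A reader might also infer that the plan inflates the drug effect. It does not do so in general: a sample before full effect usually dilutes the reduction. The fault is a mislabelled time point and wrong analysis-set entry. The change is worth making before database lock, but the point does not undermine the trial.

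**What to change.** In SAP 5.6, state that plasma oxalate samples from early-withdrawal visits are assigned by actual study day, using pre-specified windows around Days 85, 113, 141 and 169. One choice is the nearest scheduled day: Days 71-98, 99-126, 127-154 and 155-183. Day 71 is not the only defensible lower limit; the Table 1 window for Month 3 (±4 days) would give Day 81. What matters is that the limit is fixed in advance.

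A sample before the Month 3 window is labelled early termination and listed. It is not used for the Month 3 to Month 6 estimate, for Full Analysis Set entry under SAP 4.1 or for the completion count in SAP 6.1.

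Echocardiogram and quality of life have their only post-baseline assessment in this period at Month 6. Flag early values of these with their study day; automatic exclusion could remove a patient's only post-baseline result.

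The cost is a few lines of SAP text and programming. The downside is that a very early leaver drops out of the Full Analysis Set and appears only in the Safety Analysis Set sensitivity analysis.
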